## 5.5 Criteria for Removal from Study

Patients will be removed from study when any of the criteria listed in Section 5.3 applies. The reason for study removal and the date the patient was removed must be documented in the Case Report Form.

## 5.6 Criteria to Resume Treatment

Some patients may continue to benefit from treatment, maintaining or improving responses after progression including those treated with steroids.

Restarting applies only to Grade 2 events and some Grade 3 events (skin rash and thyroiditis).

For non-autoimmune or non-inflammatory events, patients may resume treatment with study drug when the drug-related AE(s) resolve to Grade  $\leq 1$  or baseline value, with the following exceptions:

- Patients may resume treatment in the presence of Grade 2 fatigue.
- Evaluation to exclude any additional immune mediated events endocrine, GI, and liver / pancreas function as clinically indicated must be made prior to restarting.
- Non-drug-related toxicity including hepatic, pulmonary toxicity, diarrhea, or colitis, must have resolved to baseline before treatment is resumed.

If the criteria to resume treatment are met, the patient should restart treatment no sooner than the next scheduled time point per protocol. However, if the treatment is delayed past the next scheduled time point per protocol the treatment should resume at the earliest convenient point that is within the 6 week delay period.

If treatment is delayed for > 6 weeks, (> 8 weeks for patients on a steroid taper), the patient must be permanently discontinued from study therapy, except as specified in Section 5.3.

For patients treated with corticosteroids:

- Grade 2 events must resolve to  $\leq$  Grade 1 before considering retreatment.
- Grade ≥ 2 events should have nivolumab held until resolution to ≤ Grade 1 for at least 2 weeks following complete removal from steroid treatment except for maintenance replacement doses for adrenal insufficiency (preferably no greater than 10mg prednisone equivalent daily).
- Grade  $\geq$  3 events should have nivolumab discontinued. Patients with Grade 3 thyroiditis and skin rash may continue therapy as for Grade 2 events with resolution and stable

replacement treatment.

Patients with hepatitis, pancreatitis, pneumonitis, and colitis are at risk for exacerbation with retreatment if there is residual inflammation and should resolve to Grade 0 or baseline before retreatment. Baseline can mean the initial grade *i.e.* Grade <1 where permitted on study.

Patients with thyroiditis or hypopituitarism who are stable as above may be restarted with replacement hormones including thyroid hormone and physiologic doses only of corticosteroids. Please note that grading for hypophysitis with symptoms of headache, visual or neurologic changes or radiologic evidence of pituitary enlargement and other CNS events such as aseptic meningitis or encephalitis should be considered Grade 3 events.

New immune related events or exacerbation of existing events during steroid treatment or taper suggest the presence of ongoing immune activation and should require permanent discontinuation of nivolumab.

A patient who is treated with steroids, evaluated, and found to not have an autoimmune or inflammatory event requiring steroid treatment, may be restarted if asymptomatic off steroids for 2 weeks and other restarting criteria are met.

Prior to starting corticosteroids or hormone replacement for any reason, appropriate endocrine testing including cortisol, ACTH, TSH and T4 must be drawn if clinically feasible to document baseline function and distinguish the pituitary from peripheral organ dysfunction and later from steroid (or thyroid) treatment associated ACTH (or TSH) suppression. Steroids should be started prior to obtaining results based on clinical indications.

# 5.7 Treatment of Nivolumab-Related Infusion Reactions

Since nivolumab contains only human immunoglobulin protein sequences, it is unlikely to be immunogenic and induce infusion or hypersensitivity reactions. However, if such a reaction were to occur, it might manifest with fever, chills, rigors, headache, rash, urticaria, angioedema, pruritus, arthralgia, hypo- or hypertension, bronchospasm, or other symptoms.

All Grade 3 or 4 infusion reactions should be reported as an SAE if criteria are met. Infusion reactions should be graded according to NCI CTCAE version 4.0 guidelines.

Treatment recommendations are provided below and may be modified based on local treatment standards and guidelines as medically appropriate:

#### For Grade 1 symptoms:

(Mild reaction; infusion interruption not indicated; intervention not indicated)

Remain at bedside and monitor subject until recovery from symptoms. Infusion rate may be slowed. If the infusion is interrupted, then restart the infusion at 50% of the original infusion rate when symptoms resolve; if no further complications ensue after 30 minutes, the rate may be

increased to 100% of the original infusion rate. Monitor patient closely.

The following prophylactic premedications are recommended for future infusions: diphenhydramine 50 mg (or equivalent) and/or paracetamol 325 to 1000 mg (acetaminophen) at least 30 minutes before additional nivolumab administrations, slowing infusion rate as above.

## For Grade 2 symptoms:

(Moderate reaction requires therapy or infusion interruption but responds promptly to symptomatic treatment [e.g., antihistamines, non-steroidal anti-inflammatory drugs, narcotics, corticosteroids, bronchodilators, IV fluids]; close observation for recurrence and treatment medications may need to be continued for 24-48 hours).

Stop the nivolumab infusion, begin an IV infusion of normal saline, and treat the subject with diphenhydramine 50 mg IV (or equivalent) and/or paracetamol 325 to 1000 mg (acetaminophen); remain at bedside and monitor patient until resolution of symptoms. Corticosteroid or bronchodilator therapy may also be administered as appropriate. If the infusion is interrupted, then restart the infusion at 50% of the original infusion rate when symptoms resolve; if no further complications ensue after 30 minutes, the rate may be increased to 100% of the original infusion rate. Monitor patient closely. If symptoms recur, then no further nivolumab will be administered at that visit. Administer diphenhydramine 50 mg IV, and remain at bedside and monitor the patient until resolution of symptoms. The amount of study drug infused must be recorded on the electronic case report form (eCRF).

The following prophylactic premedications are recommended for future infusions: diphenhydramine 50 mg (or equivalent) and (acetaminophen) (or paracetamol) 325 to 1000 mg should be administered at least 30 minutes before additional nivolumab administrations. If necessary, corticosteroids (recommended dose: up to 25 mg of IV hydrocortisone or equivalent) may be used.

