# For Grade 3 or Grade 4 symptoms: (Severe reaction)

(*Grade 3* symptoms: prolonged [i.e., not rapidly responsive to symptomatic medication and/or brief interruption of infusion]; recurrence of symptoms following initial improvement; hospitalization indicated for other clinical sequelae [e.g., renal impairment, pulmonary infiltrates]).

(Grade 4 symptoms: life threatening; pressor or ventilatory support indicated.)

Immediately discontinue infusion of nivolumab. Begin an IV infusion of normal saline, and treat the subject as follows. Recommend bronchodilators, epinephrine 0.2 to 1 mg of a 1:1,000 solution for subcutaneous administration or 0.1 to 0.25 mg of a 1:10,000 solution injected slowly for IV administration, and/or diphenhydramine 50 mg IV with methylprednisolone 100 mg IV (or equivalent), as needed. Patient should be monitored until the investigator is comfortable that the symptoms will not recur. Nivolumab will be permanently discontinued.

Investigators should follow their institutional guidelines for the treatment of anaphylaxis. Remain at bedside and monitor patient until recovery from symptoms.

In the case of late-occurring hypersensitivity symptoms (*e.g.*, appearance of a localized or generalized pruritus within 1 week after treatment), symptomatic treatment may be given (*e.g.*, oral antihistamine, or corticosteroids).

Please note that late occurring events including isolated fever and fatigue may represent the presentation of systemic inflammation. Please evaluate accordingly.

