Please evaluate pituitary function before beginning steroid therapy or replacement therapy of any kind. \*Note patients with thyroiditis may be retreated on replacement therapy. Patients must be evaluated to rule out pituitary disease prior to initiating thyroid replacement.

Recommended management: See Appendix E for Endocrine AE management algorithm.

Fever	Management/Next Dose for Nivolumab
$\leq$ Grade 1	Antipyretic therapy if no evidence of infection.
Grade 2	Hold until $\leq$ Grade 1. Resume at same dose level.
Grade 3	Hold until $\leq$ Grade 1. Resume at same dose level.
Grade 4	Off protocol therapy.

Patients with fever should be evaluated as clinically appropriate. Patients may experience isolated fever during infusion reactions or up to several days after infusion. Evaluation over the course of 1-2 weeks should be done for other autoimmune events that may present as fever

Renal Acute Toxicity	Management/Next Dose for Nivolumab
$\leq$ Grade 1	Hold for evaluation and treatment. Resume at same dose level.
Grade 2	Hold for evaluation and treatment until $\leq$ Grade 1. Resume at same dose level if an
	inflammatory response is excluded.
Grade 3	Hold for evaluation and treatment until $\leq$ Grade 1. Resume at same dose level if an
	inflammatory response is excluded.
Grade 4	Off protocol therapy. Evaluation and treatment.

Infusion Reaction	Management/Next Dose for Nivolumab	
$\leq$ Grade 1	No change in dose.	
Grade 2	Hold until $\leq$ Grade 1. Resume at same dose level.	
Grade 3	Off protocol therapy.	
Grade 4	Off protocol therapy.	
Patients with fever should be evaluated as clinically appropriate. Patients may experience isolated fever		
during infusion reactions or up to several days after infusion. Evaluation over the course of 1-2 weeks		
should be done for other autoimmune events that may present as fever		
Recommended management: See Section 5.8 for treatment of infusion reactions.		

Recommended management: See Section 5.8 for treatment of infusion reactions.		
Cardiac *	Management/Next Dose for BMS-936558 (Nivolumab) Cardiac Toxicities	
≤ Grade 1	Hold dose pending evaluation and observation.** Evaluate for signs and symptoms of CHF, ischemia, arrhythmia or myositis. Obtain history EKG, CK (for concomitant myositis), CK-MB. Repeat troponin, CK and EKG 2-3 days. If troponin and labs normalize may resume therapy. If labs worsen or symptoms develop then treat as below. Hold pending evaluation	

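### Section 5.7 gives two dispositions for an infusion reaction that resolves, is restarted and recurs: stop for that visit (Grade 2 block) or permanent discontinuation (Grade 3 block)

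*Combined protocol and SAP*

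**What the plan says.** Section 5.7 sorts infusion reactions into grade blocks, each with its own action.

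- **Grade 2, definition:** "Moderate reaction requires therapy or infusion interruption but responds promptly to symptomatic treatment".
- **Grade 2, restart:** "If the infusion is interrupted, then restart the infusion at 50% of the original infusion rate when symptoms resolve".
- **Grade 2, recurrence after restart:** "If symptoms recur, then no further nivolumab will be administered at that visit".
- **Grade 2, later doses:** a separate paragraph opens "The following prophylactic premedications are recommended for future infusions". It covers Grade 2 reactions in general and is not tied to recurrence.
- **Grade 3, definition:** one of the listed features is "recurrence of symptoms following initial improvement".
- **Grade 3 or 4, action:** "Nivolumab will be permanently discontinued".

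The introduction to Section 5.7 calls for grading by CTCAE version 4.0. It presents the blocks as recommendations that sites may adapt to local standards.

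The infusion reaction table in Section 6 gives "Hold until $\leq$ Grade 1. Resume at same dose level" for Grade 2 and "Off protocol therapy" for Grades 3 and 4. It does not say which row a recurrence after restart belongs to. For management it refers the reader to Section 5.8, which is Treatment Beyond Progression. The infusion reaction rules are in Section 5.7.

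**The concern.** The Grade 2 block deals with the recurrence itself and limits the stop to one visit. The next block makes the same sequence of events Grade 3 and ends treatment. Two sites that both follow the text could therefore handle the same patient in opposite ways.

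Three things depend on the answer:

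- Whether a patient with a recurrent reaction receives nivolumab again.
- The tolerability endpoint. Section 13.1 measures tolerability partly by how many patients stop treatment because of intolerable toxicity. Section 13.3 stops enrollment at 3 such patients in the first 12, 4 in the first 19, or 5 before the last patient. If a permanent discontinuation for an infusion reaction is tallied there, the case scores one under one block and nothing under the other.
- Reporting. Section 7.7 asks sites to notify the coordinating center of events of Grade 3 or higher within 24 hours, so the grade also affects what is escalated.

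**Working it through.** **Text check.** Take a patient whose Grade 2 reaction interrupts the infusion.

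1. Under the Grade 2 block the infusion restarts only after symptoms resolve. Any recurrence after restart therefore follows an improvement.
2. The Grade 2 block addresses that recurrence and stops drug for the visit. It neither ends treatment nor sends the reader to the Grade 3 rule.
3. The Grade 3 definition, read literally, includes a recurrence after improvement, and its consequence is permanent.
4. The Section 6 table agrees with Section 5.7 grade by grade (Grade 2 resumes, Grade 3 is off). It does not assign the recurrence to a row, so it does not break the tie.

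| Source | Fit to the recurrence | Disposition |
|---|---|---|
| 5.7, Grade 2 block | Names it directly | Stop limited to that visit |
| 5.7, Grade 3 or 4 block | Meets the Grade 3 definition | Permanent discontinuation |
| 6, infusion reaction table | Silent | Resume (Grade 2) or off (Grade 3) |

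**Effect on the count.** Each such case moves the discontinuation tally by 1 or by 0. With 2 other discontinuations among the first 12 patients, the tally is 2 (continue) or 3 (stop enrollment).

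**Effect on the stopping probability.** The plan prints no stopping probability, so there is no figure to reproduce. Inputs are the Section 13.3 boundaries, N = 20, one look per patient, and an assumed true discontinuation rate θ. With X the count in the first 12 patients and Y the count in the next 7:

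P(stop) = P(X ≥ 3) + Σ over x = 0, 1, 2 of P(X = x) · P(Y ≥ 4 − x)

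Patient 20 adds nothing: a trial still open after 19 patients has at most 3 discontinuations and cannot reach 5.

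At θ = 0.10:

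- P(X = 0) = 0.9^12 = 0.2824; P(X = 1) = 12 · 0.1 · 0.9^11 = 0.3766; P(X = 2) = 66 · 0.01 · 0.9^10 = 0.2301.
- P(X ≥ 3) = 1 − 0.2824 − 0.3766 − 0.2301 = 0.1109.
- For Y, binomial with n = 7: P(Y ≥ 2) = 0.1497, P(Y ≥ 3) = 0.0257, P(Y ≥ 4) = 0.0027.
- Second term: 0.2301 · 0.1497 + 0.3766 · 0.0257 + 0.2824 · 0.0027 = 0.0449.
- P(stop) = 0.1109 + 0.0449 = 0.1558.

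The same formula at the other rates:

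| θ | P(X ≥ 3) | Second term | P(stop) |
|---|---|---|---|
| 10% | 0.1109 | 0.0449 | 15.6% |
| 11% | 0.1377 | 0.0566 | 19.4% |
| 15% | 0.2642 | 0.1068 | 37.1% |

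The 10% is the rate that Section 7.7 expects. The 11% and 15% are assumptions. They correspond to an extra 0.01 · 20 = 0.2 or 0.05 · 20 = 1 patient per 20 treated whose only reason for discontinuing is a recurrence after restart.

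**The case against.** The strongest reply is that the blocks can be read in sequence. CTCAE grading gives each event one grade. The recurrence meets the Grade 3 wording, so it is regraded, and Sections 5.7 and 6 both then end treatment. On this reading the Grade 2 sentence is only a bedside instruction, which permanent discontinuation also satisfies. This is a coherent reading, and a site may well adopt it. But the regrading step is not written anywhere. Limiting the stop to one visit, inside the Grade 2 block, suggests the opposite.

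A reader might infer that the protocol orders re-dosing after a recurrence, so that the patient is at once on and off therapy. The documents do not go that far. The premedication paragraph covers Grade 2 reactions generally, and nothing in the Grade 2 block says that a patient with a recurrence must be dosed again.

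A reader might also treat the Section 6 table as a third conflicting rule. It is silent on the case. Its pointer to 5.8 is a separate editorial slip; Section 6 also cites 5.7 for the criteria to resume treatment, which are in 5.6, so both references are one number too high.

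The latitude in the Section 5.7 introduction stands as mitigation, as does Section 5.3, which lets the investigator end treatment for an adverse event judged to carry substantial risk. Neither says what the protocol default is.

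Finally, the stopping probabilities rest on assumed rates. Section 5.7 describes infusion reactions as unlikely. Section 7.1 lists them in the category of up to 20%, for any infusion reaction. No figure is given for recurrence after restart.

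**Conclusion.** The inconsistency holds on the plain text. For a reaction that resolves, is restarted and recurs, the two blocks of Section 5.7 support different dispositions, and no section states which governs. It is an unstated grading step rather than two rules that cannot be reconciled, and local latitude softens it.

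The size is one discontinuation per case, provided that permanent discontinuation for an infusion reaction is tallied as intolerable toxicity under Sections 13.1 and 13.3. The effect on the chance of an enrollment stop is unknown. Over the assumed shifts it runs from 15.6% to 19.4% (one point) or 37.1% (five points). A reader might take 37.1% as the expected consequence; the documents support no rate for these recurrences, so it is only the upper end of an illustration. The conflict itself does not depend on these figures. It should be fixed because it governs re-exposure and a primary endpoint count, and because the correction is simple.

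**What to change.** Reconcile the Grade 2 and Grade 3 or 4 blocks of Section 5.7, and the infusion reaction table in Section 6, so that a recurrence after restart has one stated grade and one stated consequence. Which grade and consequence apply is for the sponsor and investigators to decide; this review takes no position.

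In the same amendment, correct the table's reference from Section 5.8 to Section 5.7, and state in Section 13.3 how the case enters the discontinuation tally, consistent with the consequence chosen.

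The cost is one clarifying sentence in Section 5.7, a matching entry in the Section 6 table, one corrected cross-reference and a short counting note in Section 13.3. The sample size and the printed boundaries do not change.

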# For Grade 3 or Grade 4 symptoms: (Severe reaction)

(*Grade 3* symptoms: prolonged [i.e., not rapidly responsive to symptomatic medication and/or brief interruption of infusion]; recurrence of symptoms following initial improvement; hospitalization indicated for other clinical sequelae [e.g., renal impairment, pulmonary infiltrates]).

(Grade 4 symptoms: life threatening; pressor or ventilatory support indicated.)

Immediately discontinue infusion of nivolumab. Begin an IV infusion of normal saline, and treat the subject as follows. Recommend bronchodilators, epinephrine 0.2 to 1 mg of a 1:1,000 solution for subcutaneous administration or 0.1 to 0.25 mg of a 1:10,000 solution injected slowly for IV administration, and/or diphenhydramine 50 mg IV with methylprednisolone 100 mg IV (or equivalent), as needed. Patient should be monitored until the investigator is comfortable that the symptoms will not recur. Nivolumab will be permanently discontinued.

Investigators should follow their institutional guidelines for the treatment of anaphylaxis. Remain at bedside and monitor patient until recovery from symptoms.

In the case of late-occurring hypersensitivity symptoms (*e.g.*, appearance of a localized or generalized pruritus within 1 week after treatment), symptomatic treatment may be given (*e.g.*, oral antihistamine, or corticosteroids).

Please note that late occurring events including isolated fever and fatigue may represent the presentation of systemic inflammation. Please evaluate accordingly.

#### 5.8 Treatment Beyond Progression

Patients are allowed to continue treatment for 4-6 weeks and reassessed. Treatment may continue up to an additional 30% total single diameter increased over baseline, if no change in performance status, no new serious adverse event, and no need for intervention. New measureable lesions are not permitted with this schema.

#### 6. DOSING DELAYS/DOSE MODIFICATIONS

There will be no dose adjustments allowed. Subjects with infusion delays > 49 days (i.e., 2 missed doses + 7 days) should discontinue the study drugs.

Please refer to Appendix E to the protocol for toxicity management algorithms which include specific treatment guidelines. These algorithms should be followed unless there are specific clinical circumstances which the treating physician indicates variations or alternative treatment is needed.

Generally, we strongly encourage early evaluation, withholding drug, and appropriate treatment as indicated in the management tables and following event specific guidelines.

ALL OTHER	ALL OTHER Management/Next Dose for Nivolumab	
EVENTS*	*Not agent related, or agent related non-immunologically mediated	
$\leq$ Grade 1	No change in dose.	
Grade 2	Hold until $\leq$ Grade 1 OR baseline. Resume at same dose level.	
Grade 3	Hold until $\leq$ Grade 1 continue at investigator discretion.	
Grade 4	Off protocol therapy.	
Recommended management: As clinically indicated.		

ALL OTHER	Management/Next Dose for Nivolumab	
EVENTS**	**Immunologically mediated	
$\leq$ Grade 1	No change in dose.	
Grade 2	Hold until $\leq$ Grade 1 OR baseline. When resolved, resume at same dose level.	
Grade 3	Off protocol therapy (exceptions noted in Section 5.3 )	
Grade 4	Off protocol therapy	
Recommended management: As clinically indicated.		

Skin Rash and Oral Lesions	Management/Next Dose for Nivolumab
$\leq$ Grade 1	No change in dose.*
Grade 2	No change in dose.* May continue on treatment at investigator discretion.
Grade 3	Hold* until $\leq$ Grade 1. Resume at same level at investigator discretion.
Grade 4	Off protocol therapy.

\*Patients with purpuric or bullous lesions must be evaluated for vasculitis, Steven-Johnson syndrome, TEN, and autoimmune bullous disease including oral lesions of bullous pemphigus/pemphagoid. Pruritus may occur with or without skin rash and should be treated symptomatically if there is no associated liver or GI toxicity. Note skin rash typically occurs early and may be followed by additional events particularly during steroids tapering.

Recommended management: See Appendix E for Skin AE management algorithm.

Liver Function AST, ALT, Bilirubin	Management/Next Dose for Nivolumab
$\leq$ Grade 1	No change in dose. May continue on treatment at investigator discretion.
Grade 2	Hold until UNL or baseline. Resume at same dose level. Consider steroid treatment > 7 days.
Grade 3	Off protocol therapy.
Grade 4	Off protocol therapy.
Continued treatment	nt of active immune mediated hepatitis may exacerbate ongoing inflammation. Holding

drug to evaluate LFT changes and early treatment are recommended.

LFT changes may occur during steroid tapers from other events and may occur together with other GI events including cholecystitis/pancreatitis.

For individuals who are hepatitis B or C positive, viral DNA or RNA load, respectively, should be measured to determine if worsening LFTs are due to immune-mediated hepatitis or infectious hepatitis. Recommended management: See Appendix E for Hepatic AE management algorithm.

Diarrhea/ Colitis	Management/Next Dose for Nivolumab
$\leq$ Grade 1	Hold until Grade 0 or baseline. When resolved, resume at same dose level.
Grade 2	Hold until Grade 0 or baseline. Consider steroid treatment > 7 days.
Grade 3	Off protocol therapy.
Grade 4	Off protocol therapy.
Patients with Grade 2 symptoms but normal colonoscopy and biopsies may be retreated after resolution.	
Patients who require steroids should be taken off study treatment.	
Please evaluate pituitary function prior to starting steroids if possible without compromising acute care.	
Evaluation for all patients for additional causes includes C. diff, acute and self-limited infectious and food	
borne illness, ischemic bowel, diverticulitis, and IBD.	

Recommended management: See Appendix E for GI AE management algorithm for management of symptomatic colitis.

Pancreatitis Amylase/Lipase	Management/Next Dose for Nivolumab
$\leq$ Grade 1	If asymptomatic without evidence of pancreatitis, liver or gallbladder disease, or new onset diabetes, may continue on treatment at investigator discretion.
Grade 2	If asymptomatic without evidence of pancreatitis, liver or gallbladder disease, or new

Pancreatitis Amylase/Lipase	Management/Next Dose for Nivolumab
	onset diabetes, may continue on treatment at investigator discretion.
Grade 3	If symptomatic, hold until Grade 0. If asymptomatic, without clinical, radiographic, or ultrasound evidence of pancreatitis, and no evidence of associated liver or gall bladder disease or new onset diabetes, may continue on treatment at investigator's discretion. Patients who develop symptomatic pancreatitis or DM should be taken off protocol therapy.
